7.4 Safety Analyses

Safety and tolerability will be assessed throughout the study by examination of AEs, ophthalmic examinations, clinical laboratory tests, vital signs, and physical examinations (Stage 1). Safety related tables and listings will be based on the Safety Analysis Set.

7.4.1 Adverse Events

An AE is any untoward medical occurrence in a subject, temporally associated with the use of study product, whether or not considered related to study drug. All AEs will be coded using MedDRA version 24.1 or later.

A TEAE is defined as any AE with onset on or after the first dose of study drug, until 30 days after last dose.

A study drug related AE is defined as an AE classed as “Possibly Related” or “Related” to the study drug. If an AE has missing causality, it is assumed to be related to the study drug for analysis purposes.

Multiple events will be counted once per subject in each summary level.

Any AE that has worsened in the severity will be recorded as a separate AE.

To evaluate the incidence of TEAEs, the number and percent of subjects who experienced a TEAE within each SOC or PT summary level will be summarized by treatment group. Subjects will only be counted once within each summary level. In addition, the total number of TEAEs within a summary level will be presented. A subject is counted at most once per SOC and PT at the maximum severity for TEAE summary by maximum severity. AEs with missing severity will be classified as “Severe.”

An overall summary table of TEAEs will include:

- Any TEAEs
- Serious TEAEs
- TEAEs related to study drug
- TEAEs leading to discontinuation of study drug
- Ophthalmic TEAEs

TEAEs will be summarized by treatment group (including overall), for:

- TEAEs by SOC and PT
- Serious TEAEs by SOC and PT
- Related TEAEs by SOC and PT
- TEAEs by SOC, PT, and maximum severity
- TEAE leading to discontinuation of study drug by SOC and PT
- Ophthalmic TEAEs by SOC and PT (study eye and fellow eye summarized separately)

AEs listings will be presented by treatment group, subject, start date, SOC and PT for:

- All AEs
- Serious AEs
- AEs leading to discontinuation of study drug

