	
 
4. Ocular trauma within 6 months prior to screening or non-invasive laser treatment within the 3 months prior to screening
 
5. Use of any ocular medication in either eye within 14 days of screening and throughout the study, with the exception of a) lid scrubs (which may be used prior to, but not after, screening), b) lubricating drops for dry eye (which may be used throughout the study no more than 2 times per day and at least 10 minutes between the study drug and the lubricating eye drop)
 
6. Use of contact lenses in the study eye. Contact lenses wearers must discontinue wearing at least 3 days prior to Day 1 visit and throughout the study
 
7. Known hypersensitivity to benzalkonium chloride or excipients of RMP-A03 ophthalmic solution
 
8. Cannot demonstrate proper delivery of eye drops, or, in the investigator's opinion, unable to deliver eye drops consistently
 
 
Systemic:
 
 
9. Clinically significant abnormalities in laboratory tests at screening
 
10. Clinically significant systemic disease which may place the participant at risk or confound study results
 
11. Participation in any investigational study within 30 days prior to screening
 
12. Female participants who are pregnant, or females of childbearing potential who are pregnant, nursing, planning a pregnancy, or not using a medically acceptable form of birth control (see Section 5.6). Females of childbearing potential must have a negative pregnancy test at baseline
 

Duration of Treatment	7 days in stage 1; 28 days in stage 2
Endpoints	
Primary Efficacy Endpoint:
 
 
• Change from baseline in pterygium hyperemia grading at Day 28
 
 
Secondary Efficacy Endpoints:
 
 
• Change from baseline in pterygium characteristics at Day 28 
 
○ length
 
○ encroachment onto the cornea
 
○ size at limbus
 
 
 

	
[REDACTED]
 
[REDACTED]
 
[REDACTED]
 
[REDACTED]
 
[REDACTED]
 
Safety:
 
 
• Incidence of AEs
 

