**Note, intrasubject escalation will not be permitted.**

**Stage 2** will initiate upon completion of Stage 1 and following determination of MTD among the 4 evaluated doses. Stage 2 is a randomized, doubled-masked, placebo-controlled study

comparing the efficacy and safety of RMP-A03 with placebo in patients with pterygium. Approximately 75 patients are planned to be randomized to 1 of 3 treatment groups in a 1:1:1 ratio. These treatment groups will consist of the 2 doses of RMP-A03 and the RMP-A03 vehicle. A single eye drop of RMP-A03 or RMP-A03 vehicle will be applied TID to the study eye for a total of 28 days. Patients will be followed for a total of 84 days. The study will consist of 7 visits as follows: Screening (up to 60 days prior to the baseline visit), Baseline/Day 1, Day 7, Day 14 (Phone Visit), Day 28, Day 56, and Day 84 (see Table 1-2 for study visits and procedures and Figure 1 for the study schematic).

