### **8.4.1. ADVERSE EVENTS**

Qualified study staff responsible for assessing adverse events (AEs) will be listed on the Delegation of Responsibilities Log. This includes assessment of AE severity and relationship to study medication. Adverse event information may be volunteered by the subject or solicited by study personnel through non-leading questions.

All AEs occurring during the study, regardless of the assumption of causal relationship, must be documented on the respective CRF. Documentation of AEs/adverse reactions includes start date and stop date, severity, action(s) taken, seriousness and outcome (See Section 10).

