### 8.4.4. CLINICAL LABORATORY TESTS

The following clinical laboratory tests will be performed at Screening and Day 7 during Stage 1 and at Screening and Day 84 (Exit visit)/or Early Exit during Stage 2. Fasting is required prior to specimen collection during Stage 1.

- Complete blood count: hematocrit, hemoglobin, mean corpuscular hemoglobin, mean corpuscular volume, mean platelet volume, platelet count, red blood cell count, and white blood cell count with differential (absolute).
- Clinical chemistry: alanine aminotransferase, aspartate aminotransferase, alkaline phosphatase, total bilirubin, amylase, lipase, calcium, magnesium, glucose, sodium, potassium, carbon dioxide, chloride, blood urea nitrogen, and creatinine.
- Urinalysis: dipstick test and a microscopic examination if clinically indicated.

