### **10. ADVERSE EVENTS**

#### **10.1. ADVERSE EVENT DEFINITIONS**

##### **10.1.1. ADVERSE EVENT**

An adverse event (AE) is defined as any untoward medical occurrence associated with the use of a drug in humans, whether or not considered drug related. An AE can be any unfavorable and unintended sign (e.g., an abnormal laboratory finding), symptom, or disease temporally associated with the use of a drug, and does not imply any judgment about causality.

AEs will be coded using the medical dictionary for regulatory activities (MedDRA). Frequencies and percentages of AEs will be summarized at the subject level by system organ class (SOC) and preferred term (PT). An AE is treatment emergent (TEAE) if it occurs or worsens after the first dose of study medication. Similar summaries will be presented for all TEAEs. Separate summaries will be performed for ocular and non-ocular AEs.

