### **10.5. DOCUMENTATION OF ADVERSE EVENTS BY INVESTIGATOR**

Subjects will be evaluated and questioned generally to identify AEs during the course of the study. Any events occurring prior to administration of the first dose will be recorded on the Adverse Event CRF as pre-treatment adverse event. Events occurring after administration of the first dose of study drug will be recorded on the Adverse Event CRF as TEAE.

Record all AEs spontaneously reported by the subject and/or in response to an open question from study personnel or revealed by observation, physical examination, or other diagnostic procedures on the Adverse Event Form for that visit. Any clinically relevant deterioration in laboratory assessments or other clinical findings is considered an AE and must be recorded on

the Adverse Event Form. In addition, an abnormal test finding must be classified as an AE if one or more of the following criteria are met:

- The test finding is accompanied by clinical symptoms
- The test finding necessitates additional diagnostic evaluation(s) or medical/surgical intervention; including significant additional concomitant drug treatment or other therapy. (Note: simply repeating a test finding, in the absence of any of the other listed criteria, does not constitute an AE)
- The test finding leads to a change in study drug dosing or discontinuation of subject participation in the clinical research study
- The test finding is considered an AE by the Investigator

Wherever possible, a specific disease or syndrome rather than individual associated signs and symptoms should be identified. However, if an observed or reported sign or symptom is not considered a component of a specific disease or syndrome by the Investigator, it should be recorded as a separate AE. Laboratory data are to be collected as stipulated in this protocol. Clinical syndromes associated with laboratory abnormalities are to be recorded as appropriate (e.g., diabetes mellitus rather than hyperglycemia).

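### The SAP ends the treatment-emergent AE window 30 days after last dose without declaring the change, so Stage 2 AEs with onset from about Day 59 to Day 84 enter no AE table

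*SAP*

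**What the plan says.** The two documents define treatment emergence differently.

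- Protocol 10.1.1: "An AE is treatment emergent (TEAE) if it occurs or worsens after the first dose of study medication". No end date is given.
- Protocol 10.5 applies the same open-ended rule to data capture: "Events occurring after administration of the first dose of study drug will be recorded on the Adverse Event CRF as TEAE".
- SAP 7.4.1: "A TEAE is defined as any AE with onset on or after the first dose of study drug, until 30 days after last dose".

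On output, SAP 7.4.1 introduces its SOC/PT tables with "TEAEs will be summarized by treatment group (including overall), for". The tables that follow (all, serious, related, by maximum severity, leading to discontinuation, ophthalmic) and the overall summary table are all restricted to TEAEs. Only the listings cover all AEs and all serious AEs. Protocol 10.1.1, by contrast, calls for SOC/PT summaries of AEs as well as similar ones for TEAEs.

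On timing, the protocol synopsis gives treatment duration as "7 days in stage 1; 28 days in stage 2". For Stage 2, Protocol 4.1 says "Patients will be followed for a total of 84 days". Collection covers the whole period (Protocol 8.4.1): "All AEs occurring during the study, regardless of the assumption of causal relationship, must be documented on the respective CRF". Laboratory tests are done "at Screening and Day 84 (Exit visit)/or Early Exit during Stage 2" (Protocol 8.4.4).

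SAP Section 8 lists one change from the protocol, the baseline covariate in the efficacy models. It does not mention the TEAE window or the absence of all-AE tables.

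**The concern.** Safety and tolerability is the primary objective of this first-in-human study, and AE incidence is its safety endpoint. The protocol follows Stage 2 patients for eight weeks after dosing and collects AEs throughout. The SAP then tabulates only about the first 30 days of that off-drug period.

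A Stage 2 AE with onset on Day 70 would be a TEAE under the protocol and on the CRF, but not in the analysis. Even if serious or judged related, it would enter no by-arm count. The reported incidence would be lower than the protocol's own definition gives, and a reader of the tables would have no notice that the definition had changed.

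Laboratory findings are the most exposed. Protocol 10.5 requires clinically relevant laboratory deterioration to be recorded as an AE, yet for a completer the only scheduled post-baseline draw is at Day 84. SAP 7.4.3 lists laboratory values without summarizing them, so no laboratory table would pick up what the AE tables omit.

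**Working it through.** The plan gives no figure to reproduce on this point. The check is day arithmetic.

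**Inputs**
- First dose is Day 1 (SAP 7.1.3).
- Last dose in Stage 2 is taken as Day 28 (28 days of treatment, protocol synopsis).
- The window ends at last dose + 30 days (SAP 7.4.1).
- Exit is Day 84, with a visit window of ±5 days, so Day 79 to Day 89 (Stage 2 visit schedule).

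**Base case**
- Window closes: 28 + 30 = Day 58.
- Follow-up after dosing: 84 − 28 = 56 days.
- Days outside the window: 84 − 58 = 26 (Day 59 to Day 84).
- Share of all follow-up: 26/84 = 31%.
- Share of follow-up after dosing: 26/56 = 46%.

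**Sensitivity.** The documents do not fix the day of last dose for each patient. As an assumption, let it range over the Day 28 ±3 visit window, Day 25 to Day 31.

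| Last dose | Window closes | Days outside, exit Day 79 | Exit Day 84 | Exit Day 89 |
|---|---|---|---|---|
| Day 25 | Day 55 | 24 | 29 | 34 |
| Day 28 | Day 58 | 21 | 26 | 31 |
| Day 31 | Day 61 | 18 | 23 | 28 |

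Between 18 and 34 days are uncovered, and the exit visit with its laboratory draw lies outside the window in every cell. A patient who stops drug early but stays in follow-up has more uncovered time: last dose on Day 7 closes the window at Day 37 and leaves 84 − 37 = 47 days.

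**Stage 1.** Exit is at Day 7 (+1 day), well inside 30 days after last dose, so nothing is lost.

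**Laboratory AEs.** The SAP rule works on onset date, which gives three cases:
1. A completer has a new AE whose onset is dated to the Day 84 draw: outside the window, in listings only.
2. An AE is found at the Day 84 draw but its onset is dated on or before about Day 58: inside the window, tabulated.
3. A patient exits early and the draw falls within 30 days of last dose: inside the window, tabulated.

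**Under the protocol definition.** A window through study exit covers Day 1 to Day 84 and leaves no follow-up day uncovered.

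**The case against.** Much can be said for the SAP.

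- **An end to the window is a defensible choice.** The nonclinical summary (Protocol 2.3) describes negligible systemic exposure after instillation, and counting events 31 to 56 days off drug adds background noise. Protocol 9.8.4 leaves the full details of the safety analyses to the SAP. This supports showing the periods separately. It does not support changing a protocol definition without an entry in Section 8 and without any table for the later period, and the vehicle arm already shows the background rate.
- **Thirty days appears in the protocol's SAE reporting rule (10.6.1).** There it is an additional duty beside reporting of all SAEs during the study, and it does not define treatment emergence.
- **The events remain in the report.** The all-AE and serious-AE listings show them by treatment group, and with about 25 subjects per arm a reader could count them. That is true, but a listing gives no incidence and no side-by-side comparison.
- **The Day 84 eye examinations are not lost.** A reader might infer that the cut-off removes the exit visit from the analysis. It does not: SAP 7.4.2 summarizes BCDVA, IOP, slit lamp, fundus and Ocular Comfort Index at each visit with no TEAE filter.
- **Not everything found at the Day 84 draw is lost.** A reader might infer that it is. The onset-date rule and the early-exit draws rule that reading out.
- **A wider window does not cure the laboratory schedule.** The lack of a scheduled Stage 2 draw between Screening and Day 84, and the listing-only laboratory output (although Protocol 9.8.4 says these data will be summarized), are separate matters.
- **Worsening is not dropped within the window.** SAP 7.4.1 records a worsened AE as a separate event.

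These points limit the scope. The undeclared difference in definition, and the absence of any table for later AEs, stand.

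**Conclusion.** The point holds for Stage 2 AE tables. The SAP narrows the protocol's TEAE definition without declaring it. With last dose at Day 28 and exit at Day 84, AEs with onset over 26 days (18 to 34 days under the assumed ranges for last dose and exit) reach no by-arm count. For completers this includes any new AE dated to the Day 84 laboratory draw.

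The 31% and 46% are shares of calendar time, not of events. The documents give no late-event rate, so the number of AEs affected cannot be estimated. A reader might also infer that the comparison between arms is biased. The documents do not support that: the same rule applies to all three arms, and nothing shows that late events would differ between them. What is affected is the completeness of the reported incidence against the protocol's definition.

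Because the data are collected and listed, and the remedy is small, this is a change that should be made rather than a fatal defect.

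**What to change.** In SAP 7.4.1, take one of two routes:

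1. Align the TEAE window with the protocol, so that it covers onset or worsening from first dose through study exit, and split the AE tables into the period up to 30 days after last dose and the period after it.
2. Keep the 30-day cut-off, add by-arm SOC/PT tables of AEs with later onset, including serious and related ones, and list the narrower definition in SAP Section 8 with its reason.

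No new data are needed. The cost is a change of SAP wording and one extra column or table. Under the first route some late background events enter the overall count; the split by period and the vehicle arm make them visible.

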7.4.2 Ophthalmic Evaluations

Fellow (non-study) eye for all subjects will be pooled as an additional treatment group for summary analyses.

7.4.2.1 Best-Corrected Distance Visual Acuity (BCDVA)

Baseline, and post-baseline BCDVA values (“20/n” for Snellen, where n is the smallest line read correctly) will be summarized by treatment group and visit for both the Snellen and ETDRS (early treatment diabetic retinopathy study) charts.

A listing of BCDVA results and manifest refraction measurements will also be provided.

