#### **9.8.4. SAFETY ANALYSES**

All untoward physical findings/laboratory results identified prior to initiation of study drug will be reported on the medical history and/or physical examination CRFs. After initiation of study drug, any clinically significant changes in physical findings/laboratory results or any new physical findings/laboratory results will be evaluated for AEs.

All safety endpoints including AEs, visual acuity, intraocular pressure, slit lamp biomicroscopy, dilated fundus exam, laboratory evaluations, and vital signs will be summarized by treatment group and visit using continuous and categorical summary statistics as appropriate. Changes or shifts from Baseline will also be summarized where appropriate. For assessments performed by eye, study eye and fellow eye will be summarized separately. If necessary, the safety data will be summarized by study eye and fellow eye separately.

Full details of the safety analyses will be specified in the study SAP.

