7.4.3 Clinical Laboratory Values

All clinical laboratory tests (hematology, chemistry, urinalysis, and other) will be listed. Abnormal laboratory results and/or with clinical significance will be flagged.

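### The SAP gives no by-arm laboratory summary, no within-subject change in visual acuity and no by-arm fellow-eye examination data, and Section 8 declares none of this as a departure from Protocol 9.8.4

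*SAP*

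**What the plan says.** Protocol 9.8.4 covers all safety endpoints and names visual acuity among them. It ends its list with "laboratory evaluations, and vital signs will be summarized by treatment group and visit using continuous and categorical summary statistics as appropriate". It continues "Changes or shifts from Baseline will also be summarized where appropriate" and "For assessments performed by eye, study eye and fellow eye will be summarized separately", and it hands the detail on: "Full details of the safety analyses will be specified in the study SAP".

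The SAP then specifies:

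- **Laboratory values (7.4.3):** "All clinical laboratory tests (hematology, chemistry, urinalysis, and other) will be listed", with abnormal or clinically significant results flagged. No summary table is planned.
- **Visual acuity (7.4.2.1):** values before and after dosing (20/n for Snellen, "where n is the smallest line read correctly) will be summarized by treatment group and visit for both the Snellen and ETDRS" charts. Also, "A listing of BCDVA results and manifest refraction measurements will also be provided". There is no change from baseline, no shift table and no count of lines lost.
- **Fellow eyes (7.4.2):** "Fellow (non-study) eye for all subjects will be pooled as an additional treatment group for summary analyses".

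SAP Section 8, which records changes from the protocol, has one entry. It concerns the baseline hyperemia covariate in the efficacy models. No safety item appears there.

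**The concern.** Safety and tolerability is the primary objective in both documents, so the safety tables carry the main result. Three things the protocol leads a reader to expect are absent, and no reason is given.

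The laboratory gap is the plainest. A summary by arm and visit is promised without qualification, and only a listing is planned.

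The acuity gap is narrower but hard to explain. The SAP gives change from baseline for every other quantitative ophthalmic or vital-sign measure, and Protocol 4.2 defines its first safety threshold as a within-subject loss of 3 or more lines. No planned table shows that quantity.

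The fellow-eye point is the smallest. Pooling removes the vehicle comparison for examination findings in the undosed eye, which is where a contralateral or systemic effect would appear.

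At stake is whether the report's tables let a reader compare the arms on vision loss and laboratory change, or leave that to hand work on listings.

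**Working it through.** The documents state no safety figure, so there is nothing to reproduce. The check is a comparison of texts followed by three small calculations.

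**1. Comparison of texts**

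| Measure | SAP section | By arm and visit | Change from baseline |
|---|---|---|---|
| IOP | 7.4.2.2 | yes | yes |
| Cup-to-disc ratio | 7.4.2.4 | yes | yes |
| Ocular Comfort Index | 7.4.2.5 | yes | yes |
| Vital signs | 7.4.4 | yes | yes |
| BCDVA | 7.4.2.1 | yes | no |
| Laboratory values | 7.4.3 | no (listing only) | no |

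The IOP, slit-lamp and fundus listings flag clinically significant results. The BCDVA listing is not said to do so.

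**2. What a table of raw acuity values shows**

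Inputs: 25 subjects per arm (SAP 9), a 3-line loss, and 3 subjects, the smallest number above 2 (Protocol 4.2). Assume the other eyes in the arm do not change and no values are missing.

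- Shift in the arm mean = m × 3 / 25 lines; proportion with the loss = m / 25.
- m = 1: 0.12 line, 4%.
- m = 2: 0.24 line, 8%.
- m = 3: 0.36 line, 12%.

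The mean of the changes would move by the same 0.36 line, so the line-loss count is what makes the losses visible. A change table helps in a second way: SAP 7.1.1 reports minimum and maximum, so the largest individual loss would appear.

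Change is not automatically more precise than the raw value. With equal variance at both visits, SD(change)/SD(raw) = √(2(1 − ρ)). The documents give no correlation. For ρ = 0.5, 0.7, 0.8 and 0.9 the ratio is 1.00, 0.77, 0.63 and 0.45, so change gains precision only when ρ exceeds 0.5.

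**3. Whether the adverse event tables close the gap at Day 84**

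Inputs: 28 days of dosing; treatment-emergent status ends 30 days after the last dose (SAP 7.4.1); final visit at Day 84 ± 5; Stage 2 laboratory tests only at Screening and Day 84 or early exit (Protocol 8.4.4).

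- End of the window = 28 + 30 = Day 58. If the last dose were as late as Day 31, the top of the Day 28 visit window, it would be Day 61.
- Earliest in-window final visit = 84 − 5 = Day 79, which is 21 days after Day 58, or 18 days after Day 61.

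For a completer, an abnormality first found and dated at the final visit is therefore not treatment-emergent under the SAP. The planned event tables count treatment-emergent events only. A laboratory finding would reach listings alone, and an acuity loss would enter a by-arm table only as a raw value. The protocol's own definition of treatment-emergent (10.1.1) has no end date.

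**4. Fellow eyes**

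Under 1:1:1 allocation, an effect confined to one dose arm is diluted to 1/3 of its size in the pooled group, and an effect in both dose arms to 2/3. No vehicle fellow-eye group is left for comparison.

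**The case against.** The best defence is that the protocol leaves room. Changes and shifts are promised only where appropriate, and the detail is delegated to the SAP. For acuity this has some force, because the missing item lies within that discretion. It does not cover the laboratory data: the by-arm, by-visit summary carries no such qualifier, and delegating detail is not permission to drop a table.

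A second defence is that little would be lost. By-subject listings are sorted by treatment group. Clinically relevant laboratory deterioration must be recorded as an adverse event. Stage 1 cohorts have up to 5 subjects, so a flagged listing can be read directly. Stage 2 laboratory tests come 84 − 28 = 56 days after dosing ends, so a by-arm table says little about on-treatment effects in completers. Only the study eye is dosed, and Protocol 2.3 reports negligible systemic exposure in nonclinical work. All of this stands and limits the consequence. It does not supply the promised comparison, and the Day 84 calculation shows that the event tables are not a full substitute.

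A reader might also infer more than the documents support:

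- **That the by-arm acuity summary is gone.** It is kept; only change and line loss are missing.
- **That the missing table disables the stopping rule, or that one 3-line loss meets it.** The criterion needs drug-related loss in more than 2 subjects, and the safety committee applies it to all available safety data, not to the final tables.
- **That averaging the Snellen denominator would mislead.** The SAP does not say n is averaged; the lines could be tabulated by category, and ETDRS results are summarised as well.
- **That fellow-eye adverse events lose their arm.** SAP 7.4.1 tabulates ophthalmic treatment-emergent events by treatment group, separately for each eye. The pooling sentence sits under the examinations.

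**Conclusion.** The point holds in three parts of unequal weight. The laboratory departure is a direct conflict with Protocol 9.8.4, though of limited consequence given when the samples are taken. The missing acuity change and line-loss count is a real gap for a primary safety objective: losses in 3 of 25 eyes, 12% of an arm, would move the arm mean by only 0.36 line. Pooling fellow eyes is a lesser matter affecting examination summaries only. None of the three is declared in SAP Section 8.

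The 0.36-line figure assumes exactly 3 lines lost per affected eye and no change in the rest. The Day 84 argument assumes a subject who completes dosing on schedule and an event dated when it was found; it need not apply to early exits. The finding is about what the planned tables can show. It does not imply that individual safety data go unreviewed, since listings and event recording remain.

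**What to change.** - **SAP 7.4.2.1:** add change from baseline in BCDVA, in ETDRS letters or logMAR, and the number and percentage of eyes losing 3 or more lines, by arm and visit.
- **SAP 7.4.3:** add laboratory summaries by arm and visit, with change from baseline and normal/abnormal shift tables.
- **SAP 7.4.2 (lesser point):** summarise fellow eyes by the subject's own treatment group or dose cohort.
- **SAP Section 8:** list and justify any of these departures that is kept.

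The cost is SAP wording and a few extra tables from data already collected, with no change to visits or procedures. The Stage 2 laboratory tables should carry a note that the samples are from Screening and Day 84 or early exit, so that they are not read as evidence about the dosing period.
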